Appendix G Participant Follow-up

Appendix G1. Participant 6-month Follow-up Questionnaire

Hi, my name is _____. I'm calling because you kindly agreed to participate in the POW-R Health: Power to Redefine your Health Program. If you recall, part of being in the study is completing a survey—once before the study starts, and a final time after the study ends. The survey information will be used to see if our dietary intervention worked to improve your health. This phone survey will take about 45-60 minutes to complete. Do you have time to take the survey now?

If no: What would be a good day and time for me to call you? (please use Telephone Disposition Sheet)

If yes: Thank you! Please remember that everything you say here will be confidential. Your information won't be identified by name (proceed to questions below).

BLADDER CANCER FOLLOW-UP

Let's begin the survey with questions about your bladder cancer status. These questions refer to the time period since we last talked with you, which is approximately the past 6 months.

1. In the last 6 months, have you had a clinical assessment, or cystoscopy, for your bladder cancer?

1 	Yes	
0 	No	→ Skip to Question 2 (cystectomy)
8 	Don't Know	→ Skip to Question 2 (cystectomy)
9 	Refused	→ Skip to Question 2 (cystectomy)

1a. What was the date of your last assessment? _____

2. In the last 6 months, have you had a cystectomy (surgery to remove the bladder)?

1 	Yes	
0 	No	→ Skip to Question 3 (recurrence)
8 	Don't Know	→ Skip to Question 3 (recurrence)
9 	Refused	→ Skip to Question 3 (recurrence)

2a. What was the date of the cystectomy? _____

3. In the last 6 months, have you had a recurrence of your bladder cancer (i.e., did your doctor say that the original cancer came back or that you had a new lesion/mass/tumor)?

1 Yes → Skip to Question 10 (other cancer)
0 No → Skip to Question 10 (other cancer)
8 Don't Know → Skip to Question 10 (other cancer)
9 Refused → Skip to Question 10 (other cancer)

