2. BACKGROUND

The problem of bladder cancer. Bladder cancer is the sixth most common cancer in the US, contributing to over 80,000 new cases and 17,000 deaths annually². The majority of bladder cancer (70-80%) is diagnosed at an early stage with cancer confined to the epithelial and lamina propria layer of the bladder—also known as non-muscle invasive bladder cancer (NMIBC)⁴. The standard treatment for NMIBC is transurethral resection of bladder tumor, which is a routine clinic procedure without hospitalization. However, NMIBC typically recurs (50-80%) with some patients experiencing multiple recurrences at similar stages and others (20-30%) progressing to muscle-invasive disease, which is associated with cystectomy and poor survival³⁻⁵. Depending on pathological characteristics, approximately 15% of tumors are defined as high-risk and receive one or more doses of intravesical therapeutic agents⁶, of which Bacillus Calmette–Guerin (BCG) has been the gold standard for four decades⁷. Yet approximately 30% of these patients will be non-responders to BCG, and high incidence of local side effects are concerns⁷. For the majority of NMIBC patients, no other treatment is available, although they are still at risk of recurrence and progression. Current clinical management requires life-long surveillance by cystoscopy for NMIBC patients, amounting to bladder cancer being the most expensive cancer to treat per patient⁸⁻¹⁰. An estimated 696,440 people are living with bladder cancer in the US²³, the majority of which are off treatment and under surveillance. Novel, non-invasive, cost-effective strategies to control NMIBC recurrence and progression are urgently needed.

Dietary isothiocyanates (ITCs) in bladder cancer chemoprevention. Dietary ITCs are a group of phytochemicals primarily derived from cruciferous vegetables (cruciferae) with multi-faceted anti-cancer mechanisms. Our group has published 10 peer-reviewed papers¹¹⁻²⁰ involving *in vitro*, *in vivo*, and epidemiologic studies demonstrating the important role of dietary ITCs and ITC-rich cruciferae in preventing bladder cancer recurrence and progression. The four most common dietary ITCs and their primary urinary metabolites potently inhibited the growth of a panel of human

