3.1 How many recurrences have you had? _____ (Number)

[Note to Interviewer: If more than 1 recurrence, record the date of the most recent (last) recurrence here.]

3.1a. What was the date of your recurrence? _____

4. Did your recurrent bladder cancer progress to muscle-invasive disease?

1 Yes
0 No
8 Don't Know
9 Refused

5. Did your doctor use a scope to remove the recurrent bladder tumor? This procedure is called a transurethral resection.

1 Yes → Specify Date in 5a
0 No
8 Don't Know
9 Refused

5a. What was the date of transurethral resection (TURBT)? _____

6. Did you receive chemotherapy (e.g., mitomycin C, thiotapec, doxorubicin) for your bladder cancer recurrence/progression?

1 Yes
0 No
8 Don't Know
9 Refused

7. Did you receive immunotherapy (e.g., bacillus Calmette-Guerin [BCG], interferon) for your bladder cancer recurrence/progression?

1 Yes
0 No
8 Don't Know
9 Refused

8. Did you receive radiation therapy for your bladder cancer recurrence/progression?

1 Yes
0 No
8 Don't Know
9 Refused

9. Did you receive any other treatment for your bladder cancer recurrence/progression?

1 Yes → Specify treatment in 9a
0 No
8 Don't Know
9 Refused

9a. Specify other treatment received:

10. In the last 6 months, have you been diagnosed with any other types of cancer since your original bladder cancer diagnosis?

1 Yes
0 No → Skip to Question 11
8 Don't Know → Skip to Question 11
9 Refused → Skip to Question 11

10a. When did you receive this diagnosis?

10b. What was your diagnosis?

11. Overall, how would you rate your satisfaction with your current understanding of bladder cancer and its treatment?

1 Excellent
2 Very Good
3 Good
4 Fair
5 Poor
8 Don't Know
9 Refused

Now that we've gone over your bladder cancer status, we're now going to talk about your current lifestyle.

CURRENT LIFESTYLE

12. What is your present height without shoes?

 |__| ft. |__| inches

8 Don't Know
9 Refused

13. How much do you currently weigh?

_____ pounds

8 Don't Know
9 Refused

	Excellent	Very Good	Good	Fair	Poor	Don't Know	Refused
14. In general, would you say your health is:	5 	4 	3 	2 	1 	8 	9 

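### As printed, the 6-month questionnaire routes participants who report a recurrence past every question on its progression and treatment

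*Combined protocol and SAP*

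**What the plan says.** Appendix G1 opens with a block on bladder cancer status since the last contact. Questions 1 (cystoscopy) and 2 (cystectomy) share one pattern: Yes has no skip and leads to a date, while No, Don't Know and Refused skip forward.

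Question 3 asks: "In the last 6 months, have you had a recurrence of your bladder cancer". Its Yes line reads "1 Yes → Skip to Question 10 (other cancer" and its No line reads "0 No → Skip to Question 10 (other cancer". Don't Know and Refused have the same destination.

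Between Question 3 and Question 10 stand ten items:

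- 3.1 and 3.1a: number and date of recurrences. They begin "3.1 How many recurrences have you had", and an interviewer note says: "If more than 1 recurrence, record the date of the most recent (last) recurrence here".
- 4: progression. "Did your recurrent bladder cancer progress to muscle-invasive disease"
- 5 and 5a: transurethral resection and its date.
- 6 to 9a: treatment. Question 6, for example, asks "Did you receive chemotherapy (e.g., mitomycin C, thiotapec, doxorubicin) for your bladder cancer recurrence/progression". Questions 7 and 8 ask the same of immunotherapy and radiation, and 9 and 9a of any other treatment.

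Section 11 (Participant Data and Sample Collection Procedures) says that responses are keyed directly into pre-programmed REDCap forms. Those forms are not among the documents.

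**The concern.** A branch in which all four answers lead to the same place does nothing, and here it closes off the only questions that a participant with a recurrence was meant to answer. The trial would know that a participant recurred. It would not know from this form whether the disease became muscle-invasive, or whether the participant had a resection or intravesical or other treatment before giving the 6-month urine.

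Two things are at stake:

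- **Clinical course.** Section 1 states the motivating hypothesis in terms of recurrence and progression. The progression item is one of those that cannot be reached.
- **The secondary endpoint.** Section 16 wants a panel of genes that responds specifically to cruciferous vegetables, found by RNA-seq of cells shed from the bladder. A resection or intravesical treatment between baseline and month 6 acts on the same tissue and is a plausible competing explanation for a change in expression. The plan already treats recent chemotherapy and radiotherapy as relevant at entry, because the first exclusion criterion in Section 3 concerns them. The matching information after entry is what the form fails to collect.

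**Working it through.** No power or sample-size figure in the plan bears on this, so there is no stated figure to reproduce. The check is a trace of the form, a search for another source, and a rough sense of scale.

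**Step 1. Trace Question 3 as printed.**

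| Answer | Destination as printed | Destination on the pattern of Questions 1 and 2 |
|---|---|---|
| Yes | 10 | next item (3.1) |
| No | 10 | 10 |
| Don't Know | 10 | 10 |
| Refused | 10 | 10 |

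The items between are 3.1, 3.1a, 4, 5, 5a, 6, 7, 8, 9 and 9a. As printed, 0 of 10 can be reached by anyone. With the Yes skip removed, a participant with a recurrence enters the block at 3.1 and the items are reached in turn.

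**Step 2. Is this an error or a choice?** The bypassed items presuppose a recurrence, and the note at 3.1 allows for more than one. They make sense only after Yes. Together with the pattern of Questions 1 and 2, this marks the Yes skip as a routing error and not a decision to drop the block.

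**Step 3. Is the information collected elsewhere after baseline?**

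- Rest of Appendix G1: cystoscopy and date, cystectomy and date, the fact of recurrence, and other cancers with date. It does not cover bladder cancer progression, resection or drug treatment.
- Appendix D, returned with the urine: 18 questions, of which 15 are about food and one each about antibiotics, smoking and alcohol. None is about cancer treatment.
- Appendix F: treatment questions, but at baseline, so they cover only the time before the intervention.
- Appendix G2: programme feedback, cruciferous arm only.
- Appendix H, Exhibit A: registry data on first-course treatment, supplied when a case is identified for possible inclusion.
- Section 18: adverse events tracked in REDCap. This may catch some cases, but no field for recurrence treatment is described.

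**Step 4. Scale.** The documents give no 6-month recurrence rate. The intervention magazine (Appendix P) and the intervention call script (Appendix Q) give 50-80% within 5 years; Section 2 gives the same range with no time horizon. Assuming a constant hazard, the 6-month risk is 1 - (1 - p)^(0.5/5):

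- p = 0.50: 1 - 0.50^0.1 = 0.067; 80 × 0.067 = 5.4 participants.
- p = 0.80: 1 - 0.20^0.1 = 0.149; 80 × 0.149 = 11.9 participants.

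That is about 5 to 12 of 80 with a recurrence of any kind, if all 80 complete follow-up.

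**The case against.** The strongest reply has four parts.

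1. *The finding rests on one arrow in machine-read text.* Question 3 is laid out differently from Questions 1 and 2 in the extracted text, and option lists elsewhere in the questionnaires are damaged. This stands as a reason to look at the original page first. The text available is nonetheless unambiguous, since all four lines carry the instruction.

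2. *The data may not be lost.* Interviewers work in REDCap, whose branching is not shown, and an interviewer who reads the note at 3.1 might ask the block anyway. This also stands. A reader might infer that progression and treatment are never recorded. The documents show only that the printed form does not reach those items and that no other planned instrument shown asks for them.

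3. *No planned analysis uses these items.* This is correct. Recurrence, progression and treatment are not endpoints in Section 8, Section 19 sets the safety analysis as not applicable, and neither the ANCOVA nor the DESeq and GSEA analyses call for them. A reader might infer that the trial's main comparison is compromised; it is not. The bearing on RNA-seq is one of interpretation.

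4. *Serious events are captured by other means.* This is partly correct. A reader might take these items to be the only structured record of serious disease events, but cystoscopy, cystectomy, recurrence and other cancers remain on the form, and adverse events are graded and tracked. Nor do the documents support the inference that the supervising surgeon is deprived of a review by arm. Section 18 gives that surgeon guidance over reported side effects and symptoms, and describes neither a review of this questionnaire nor any review by arm.

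**Conclusion.** The form is wrong as written, and the severity is moderate. As printed, none of the ten items from 3.1 to 9a can be reached, and no other planned 6-month instrument shown replaces them. The loss is the detail on progression and treatment during the trial; the fact of recurrence, cystectomy and the primary ANCOVA are untouched. The conclusion assumes that the arrow on the Yes line is faithfully reproduced. Actual loss of data further assumes that REDCap follows the printed form.

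The figure of about 5 to 12 participants indicates scale only. It rests on a constant hazard, a five-year range quoted in patient material, and complete follow-up. The true 6-month risk depends on time since diagnosis. The figure counts any recurrence, so it does not say how many participants progressed or were treated.

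**What to change.** 1. Check the Yes line of Question 3 against the original page of Appendix G1, and check the branching in REDCap.
2. Route Yes at Question 3 to Question 3.1. Keep the skip to Question 10 for No, Don't Know and Refused.
3. If REDCap followed the printed form, re-contact everyone in both arms who answered Yes and ask items 3.1 to 9a. This needs an IRB-approved amendment and its own information sheet. The existing call-back in Sections 11 and 30, with Appendix W, cannot serve: it covers only the cruciferous arm and only programme feedback, so using it would collect clinical detail from one arm.

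The routing change is one line on the form and, if needed, one in REDCap. The interview lengthens by a few minutes, and only for participants with a recurrence. Re-contact costs an amendment and, on the scale above, at most about a dozen calls. It should be done soon, because recall of dates and treatments fades.

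An optional and separate addition is to widen Questions 6 to 9 to any bladder cancer treatment in the last 6 months and ask them of everyone. As worded they cover only treatment for recurrence or progression, so treatment given without a recurrence would still be missed after the routing is corrected.

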3.1 How many recurrences have you had? _____ (Number)

[Note to Interviewer: If more than 1 recurrence, record the date of the most recent (last) recurrence here.]

3.1a. What was the date of your recurrence? _____

4. Did your recurrent bladder cancer progress to muscle-invasive disease?

1 Yes
0 No
8 Don't Know
9 Refused

5. Did your doctor use a scope to remove the recurrent bladder tumor? This procedure is called a transurethral resection.

1 Yes → Specify Date in 5a
0 No
8 Don't Know
9 Refused

5a. What was the date of transurethral resection (TURBT)? _____

6. Did you receive chemotherapy (e.g., mitomycin C, thiotapec, doxorubicin) for your bladder cancer recurrence/progression?

1 Yes
0 No
8 Don't Know
9 Refused

7. Did you receive immunotherapy (e.g., bacillus Calmette-Guerin [BCG], interferon) for your bladder cancer recurrence/progression?

1 Yes
0 No
8 Don't Know
9 Refused

8. Did you receive radiation therapy for your bladder cancer recurrence/progression?

1 Yes
0 No
8 Don't Know
9 Refused

9. Did you receive any other treatment for your bladder cancer recurrence/progression?

1 Yes → Specify treatment in 9a
0 No
8 Don't Know
9 Refused

9a. Specify other treatment received:

10. In the last 6 months, have you been diagnosed with any other types of cancer since your original bladder cancer diagnosis?

1 Yes
0 No → Skip to Question 11
8 Don't Know → Skip to Question 11
9 Refused → Skip to Question 11

10a. When did you receive this diagnosis?

10b. What was your diagnosis?

11. Overall, how would you rate your satisfaction with your current understanding of bladder cancer and its treatment?

1 Excellent
2 Very Good
3 Good
4 Fair
5 Poor
8 Don't Know
9 Refused

Now that we've gone over your bladder cancer status, we're now going to talk about your current lifestyle.

CURRENT LIFESTYLE

12. What is your present height without shoes?

 |__| ft. |__| inches

8 Don't Know
9 Refused

13. How much do you currently weigh?

_____ pounds

8 Don't Know
9 Refused

	Excellent	Very Good	Good	Fair	Poor	Don't Know	Refused
14. In general, would you say your health is:	5 	4 	3 	2 	1 	8 	9 
15. In general, would you say your quality of life is:	5 	4 	3 	2 	1 	8 	9 

16. What is the primary source of drinking water at your current residence?

1 Private Well
2 Community Supply (tap water or water filtered at home)
3 Bottled Water
4 Other (specify): _____
8 Don't Know
9 Refused

17. Over the past 30 days, how many glasses of water per day do you usually drink?

1 Less than 1 glass
2 1-2 glasses
3 3-4 glasses
4 5 or more glasses
8 Don't Know
9 Refused

18. Over the past 30 days, how often did you typically feel the need to empty your bladder during the day?

1 More frequently than once an hour
2 Once an hour
3 Once every 2 hours
4 Once every 3-5 hours
5 Only once or twice a day
8 Don't Know
9 Refused

19. Other than being a part of the POW-R Health Program, are you currently following any other special diet?

1 Yes
0 No
8 Don't Know
9 Refused

If No, Don't Know or Refused, go to Question 21.

20. What type of special diet (check all that apply):

1 Vegetarian (with fish)
2 Vegetarian (no fish)
3 Vegan (no meat, chicken, fish, dairy, or eggs)
4 Macrobiotic
5 Paleo
6 Gluten-free
7 Atkins
10 Low Carb
11 Other (specify) _____
8 Don't Know
9 Refused

21. Do you currently smoke?

1 Yes, every day
2 Yes, some days →

21a. On how many of the past 30 days did you smoke a cigarette?

____|____| Days
8 Don't Know
9 Refused

22. On average, how many cigarettes do/did you smoke each day? (Note to interviewer: 1 pack=20 cigarettes)

____|____| Cigarettes per day

8 Don't Know
9 Refused

23. Over the last 30 days, how many days per week did you exercise for 20 minutes or more?

0 None
1 1-2 days

2 3-4 days
3 5 or more days

24. Compared to other people your age, how would you rate the level of your usual physical activity? (If currently ill, think about your activity during the years before your illness).

1 Much more active
2 More active
3 About the same
4 Less active
5 Much less active

DIETARY INTAKE

These next questions are about the fruits and vegetables you ate or drank during the **past 30 days**. Please think about all forms of fruits and vegetables including cooked or raw, fresh, frozen or canned. Please think about all meals, snacks, and food consumed at home and away from home.

25. During the past month, how many times per week did you drink 100% PURE fruit juices? Do not include fruit-flavored drinks with added sugar or fruit juice you made at home and added sugar to. Only include 100% juice.

____ times per week

26. During the past month, not counting juice, how many times per week did you eat fruit? Count fresh, frozen, or canned fruit.

____ times per week

27. During the past month, how many times per week did you eat cooked or canned beans, such as refried, baked, black, garbanzo beans, beans in soup, soybeans, edamame, tofu or lentils. Do NOT include long green beans.

____ times per week

28. During the past month, how many times per week did you eat dark green vegetables for example broccoli or dark leafy greens including romaine, chard, collard greens or spinach?

____ times per week

29. During the past month, how many times per week did you eat orange-colored vegetables such as sweet potatoes, pumpkin, winter squash, or carrots? (write number)

30. Not counting the vegetables mentioned, about how many times per week did you eat OTHER vegetables? Examples of other vegetables include tomatoes, tomato juice or V-8 juice, corn, eggplant, peas, lettuce, cabbage, and white potatoes that are not fried such as baked or mashed potatoes. (write number)

____ times per week

These next questions are about other vegetables you ate during the **past 30 days**. Please think about all meals, snacks, and food consumed at home and away from home.

(Go through table. Frame questions as, “How often did you eat raw arugula? Never, a few times per year, once per month, 2-3 times per month, once a week, twice per week, 3-4 times per week, 5-6 times per week, or every day.” If they answer never, go to the next vegetable. If they ate any amount, ask, “About how much raw arugula did you eat each time? The medium serving size is one cup of the vegetable, about the size of a baseball. Lightly cooked generally includes stir fry, sauté, microwave, short-term, e.g. less than 10 minutes, steam or bake, and thoroughly cooked includes stew, biol, or long-term, e.g. more than 10 minutes, steam or bake.)

Vegetables		Never	A Few Times Per Year	Once per month	2-3 Times per month	Once per week	Twice per week	3-4 Times per week	5-6 Times per week	Every day	How much each time?	S	M	L
Arugula	raw													
	lightly cooked (e.g. stir fry)													
	thoroughly cooked (e.g. stew)													
Broccoli	raw													
	lightly cooked (e.g. stir fry)													
	thoroughly cooked (e.g. stew)													
Broccoli sprout	raw													
	lightly cooked (e.g. stir fry)													
	thoroughly cooked (e.g. stew)													
Broccolini	raw													
	lightly cooked (e.g. stir fry)													
	thoroughly cooked (e.g. stew)													
Corn	raw													
	lightly cooked (e.g. stir fry)													
	thoroughly cooked (e.g. stew)													

Green cabbage	raw (e.g. coleslaw)											
	lightly cooked (e.g. stir fry)											
	thoroughly cooked (e.g. stew)											
Red/Purple cabbage	raw											
	lightly cooked (e.g. stir fry)											
	thoroughly cooked (e.g. stew)											
Sauerkraut	raw											
	lightly cooked (e.g. stir fry)											
	thoroughly cooked (e.g. stew)											
Carrots	raw											
	lightly cooked (e.g. stir fry)											
	thoroughly cooked (e.g. stew)											
Cauliflower	raw											
	lightly cooked (e.g. stir fry)											
	thoroughly cooked (e.g. stew)											
Brussels sprouts	raw											

	lightly cooked (e.g. stir fry)											
	thoroughly cooked (e.g. stew)											
Kale	raw											
	lightly cooked (e.g. stir fry)											
	thoroughly cooked (e.g. stew)											
Kohlrabi	raw											
	lightly cooked (e.g. stir fry)											
	thoroughly cooked (e.g. stew)											
Collard greens	lightly cooked (e.g. stir fry)											
	thoroughly cooked (e.g. stew)											
Peas	raw											
	lightly cooked (e.g. stir fry)											
	thoroughly cooked (e.g. stew)											
Mustard greens	raw											
	lightly cooked (e.g. stir fry)											
	thoroughly cooked (e.g. stew)											
Turnip	lightly cooked (e.g. stir fry)											
	thoroughly cooked (e.g. stew)											

Turnip greens	lightly cooked (e.g. stir fry)											
	thoroughly cooked (e.g. stew)											
Bok/ Pak choy	raw											
	lightly cooked (e.g. stir fry)											
	thoroughly cooked (e.g. stew)											
Chinese cabbage/ Napa	raw											
	lightly cooked (e.g. stir fry)											
	thoroughly cooked (e.g. stew)											
Daikon root	raw											
	lightly cooked (e.g. stir fry)											
	thoroughly cooked (e.g. stew)											
Celery	raw											
	lightly cooked (e.g. stir fry)											
	thoroughly cooked (e.g. stew)											
Garden cress	raw											
	lightly cooked (e.g. stir fry)											
	thoroughly cooked (e.g. stew)											
Water cress	raw											

	lightly cooked (e.g. stir fry)											
	thoroughly cooked (e.g. stew)											
Radicchio	lightly cooked (e.g. stir fry)											
	thoroughly cooked (e.g. stew)											
Radishes	raw											
	lightly cooked (e.g. stir fry)											
	thoroughly cooked (e.g. stew)											

I am now going to ask some questions about sauces and condiments you ate during the **past 30 days**. Please think about all meals, snacks, and food consumed at home and away from home.

(Go through table. Frame questions as, “How often did you eat mayonnaise? Never, a few times per year, once per month, 2-3 times per month, once a week, twice per week, 3-4 times per week, 5-6 times per week, or every day.” If they answer never, go to the next food. If they ate any amount, ask, “About how much mayonnaise did you eat each time? The size of your thumb from knuckle to tip or less? About two thumbs worth? Or more than 2 thumbs worth?”

For **horseradish**, if they consume any amount, ask, “about how much horseradish did you eat each time? Smaller than an egg, about the size of egg, or more than the size of an egg?)

SAUCES AND CONDIMENTS											Serving Size		
	Never	A Few Times Per Year	Once per month	2-3 Times per month	Once per week	Twice per week	3-4 Times per week	5-6 Times per week	Everyday	Medium Serving	S	M	L
		2 Tbsp.											
		1/4 cup											
Mayonnaise and mayonnaise-type spreads		2 Tbsp.											
Horseradish		1/4 cup											
Mustard		2 Tbsp.											
Wasabi		2 Tbsp.											

[figure not shown]
Belief into Action Scale

Circle a single number for each question below:

[figure not shown]
1. Please circle the highest priority in your life now? (most valued, prized)

1. My health and independence
2. My family
3. My friendships
4. Job, career or business
5. My education
6. Financial security
7. Relationship with God
8. Ability to travel & see the world
9. Listening to music and partying
10. Freedom to live as I choose

[figure not shown]
2. How often do you attend religious services? (circle a number below)

[figure not shown]
**3. Other than religious services, how often do you get together with others for religious reasons
(prayer, religious discussions, volunteer work, etc.)?**

[figure not shown]
4. To what extent (on a 1 to 10 scale) have you decided to place your life under God's direction?

[figure not shown]
5. What percentage of your gross annual income do you give to your religious institution or to other religious causes each year?

[figure not shown]
6. On average, how much time each day (in 24 hrs) do you spend listening to religious music or radio, or watching religious TV?

[figure not shown]
7. On average, how much time each day do you spend reading religious scriptures, books, or other religious literature?

[figure not shown]
8. On average, how much time each day do you spend in private prayer or meditation?

9. On average, how much time each day do you spend as a volunteer in your religious community or to help others for religious reasons?

10. To what extent (on a 1 to 10 scale) have you decided to conform your life to the teachings of your religious faith?

We're going to finish the survey by asking your opinion about the dietary program you got.

I'm going to read some statements about the dietary program you got. Please let me know whether you completely disagree with the statement, disagree with the statement, neither agree nor disagree with the statement, agree with the statement, or completely agree with the statement.

	Completely disagree	Disagree	Neither agree nor disagree	Agree	Completely agree
1. The diet program I received met my approval.	①	②	③	④	⑤
2. The diet program I received was appealing to me.	①	②	③	④	⑤
3. I liked the diet program I received.	①	②	③	④	⑤
4. I welcomed the diet program I received.	①	②	③	④	⑤

	Completely disagree	Disagree	Neither agree nor disagree	Agree	Completely agree
1. The diet program I received fit into my lifestyle.	①	②	③	④	⑤
2. The diet program I received was suitable to my lifestyle.	①	②	③	④	⑤
3. The diet program I received was applicable to my lifestyle.	①	②	③	④	⑤
4. The diet program I received was a good match with my lifestyle.	①	②	③	④	⑤

Feasibility of Intervention Measure (FIM)

	Completely disagree	Disagree	Neither agree nor disagree	Agree	Completely agree
1. The diet program I received was implementable in my life.	①	②	③	④	⑤
2. The diet program I received was possible to do in my life.	①	②	③	④	⑤
3. The diet program I received was doable.	①	②	③	④	⑤
4. The diet program I received was easy to use.	①	②	③	④	⑤

If you are a part of Group A, there are a few feedback questions we would like to ask you at this time, is this okay?

If you are a part of Group B, you have finished the survey! Thank you so much for your time. Do you have any questions? Again, thank you for your participation in POW-R Health!

